#### 4.4 Other tolerability and safety variables

The following other tolerability and safety variables will be analyzed:

- Time to discontinuation of BRV due to adverse drug reactions (ADRs)
- Incidence of treatment-emergent AEs and ADRs
- Incidence of serious treatment-emergent AEs and ADRs
- Incidence of ADRs leading to discontinuation of BRV

### 5 STUDY DESIGN

EP0077 is a postmarketing, multinational, multicenter, prospective NIS conducted at approximately 100 sites in approximately 10 European countries, with a 12-month Observation Period. Brivaracetam will be prescribed according to normal clinical practice and in accordance with the current SmPC in Europe for BRV (BRV indicated as adjunctive therapy in the treatment of POS with or without secondary generalization in patients 16 years of age and older with epilepsy). It is planned to include 530 patients in the study (see [Section 12.4](#)).

The patients will be followed as per current clinical practice. No additional clinical diagnostic or monitoring procedures will be applied. The use of an epilepsy/seizure diary, as standard clinical practice, is a requirement to enter the study. The selected questionnaires will be used if part of the standard clinical practice at the sites for the management of patients with epilepsy. The choice of medical treatment is made independently by the treating physician in the regular course of practice and is not influenced by the NIS protocol.

All patients (and/or their parents or legal representatives) have to accept in writing that his/her medical data will be used for the evaluation of the study results by signing a study-specific Patient Data Consent form according to local requirements.

The clinical evaluation of patients with epilepsy will be performed by the treating physician following routine clinical practice. All visits and assessments will be scheduled and conducted per routine clinical practice. It is anticipated that each patient will have approximately 4 visits during their participation in this study. These visits will consist of:

- Visit 1, Baseline, Day 1: represents the first day of BRV treatment
- Visit 2, approximately 3 months after Baseline
- Visit 3, approximately 6 months after Baseline
- Visit 4, approximately 12 months after Baseline or end of Observation Period

For patients who discontinue early, the treating physician should collect data as specified for Visit 4 as a Withdrawal Visit. Information on seizures will be collected using patient epilepsy diaries. All data to be collected at Visits 1, 2, 3, and 4 are described in [Section 17](#), [Table 17-1](#).

At those visits, the information collected by the treating physician will include data from any additional visits that the patients may have performed in between.

No formal interim analyses are planned (see [Section 12.3](#)).

The management and reporting of AEs will be handled according to international drug safety regulations and UCB procedures.

Documentation of all study assessments is to be performed by the treating physician in the study-specific electronic Case Report form (eCRF). Although the study is noninterventional in nature, every attempt must be made to assess all participating patients in the same way.

## **6 EXPECTED STUDY DURATION, PLANNED NUMBER OF PATIENTS AND SITES**

It is planned to include 530 patients (see [Section 12.4](#)).

Approximately 100 sites are planned for participation. The overall expected enrollment period is approximately 3 years, but this may vary in the different countries depending on the respective start of commercial BRV availability.

The Observation Period per patient will be up to 12 months after initiation of BRV treatment.

## **7 ANTICIPATED REGIONS AND COUNTRIES**

The study will be conducted in approximately 10 European countries with possible extension to other countries. The final selection of countries included will be dependent on the timing of the availability of commercial BRV in the different European countries.

## **8 SELECTION AND WITHDRAWAL OF PATIENTS**

### **8.1 Selection criteria**

Before any data are collected for any patient in this NIS, written data consent will be properly executed and documented.

The following selection criteria must be followed for patients entering the NIS:

1. Patient has never been treated with BRV prior to inclusion in this NIS.
2. The decision by the treating physician to prescribe BRV is made independently of the participation in the NIS.
3. A Patient Data Consent form is signed and dated by the patient or by the parent(s) or legal representative.
4. Patient is a male or female  $\geq 16$  years of age.
5. Patient has a clinical diagnosis of epilepsy with POS with or without secondary generalization.
6. Patient meets the criteria for treatment with BRV as adjunctive therapy according to the current SmPC in Europe.
7. Patient uses an epilepsy/seizure diary.

## 8.2 Withdrawal criteria

Patients are free to withdraw from the NIS at any time, without prejudice to their continued care.

Physicians are free to add or withdraw any medication or to withdraw the patient from the study at their own discretion.

If the physician elects to permanently stop BRV treatment, the patient will be withdrawn from the study.

The primary reason for withdrawal from the NIS must be documented in the patient's eCRF. When the primary reason for withdrawal is lack of effectiveness or an AE, both must be reported as described in [Section 10.1.8](#) of the protocol.

## 9 PRESCRIBED TREATMENT(S)

Patients will be treated with commercially available BRV and with commercially available AEDs, as prescribed by treating physicians, in accordance with current clinical practice.

### 9.1 Numbering of patients

Each patient will receive a 5-digit number assigned when entering the study that serves as the patient identifier throughout the study.

The patient identification list will be kept by the treating physician. Access to this list may be granted only to members of staff, authorized persons of UCB (or designees), and the competent authorities. The study monitor is also bound to confidentiality. After the end of the study, the identification list will remain with the physician.

## 10 ASSESSMENT OF SAFETY

For the assessment of safety of BRV, the causal relationship, seriousness, and outcome of AEs will be collected during the Observation Period. It is the task of the treating physician to make a judgment about a causal relationship with the BRV intake.

### 10.1 Reporting of AEs or other safety relevant information

#### 10.1.1 Definition of AEs

An AE is any untoward medical occurrence in a patient or clinical investigation patient administered a pharmaceutical product that does not necessarily have a causal relationship with this treatment. An AE can therefore be any unfavorable and unintended sign (including an abnormal laboratory finding), symptom, or disease temporally associated with the use of a medicinal product, whether or not related to BRV.

#### 10.1.2 Other safety relevant information

Other safety relevant information includes the following:

- Off-label use

This relates to situations where BRV is intentionally used for a medical purpose not in accordance with the authorized product information.

- **Misuse**  
This refers to situations where BRV is intentionally and inappropriately used not in accordance with the authorized product information.
- **Abuse**  
This corresponds to the persistent or sporadic, intentional excessive use of BRV, which is accompanied by harmful physical or psychological effects (2010/84/EU Art 1).
- **Medication error**  
For the purpose of this NIS, medication error refers to any unintentional error in the prescribing, dispensing, or administration of BRV while in the control of the healthcare professional, patient, or consumer.
- **Occupational exposure**  
This refers to the exposure to BRV (as defined in 2010/84/EU Art 1), as a result of one's professional or nonprofessional occupation.
- **Lack of therapeutic effect**
- **Overdose**  
See [Section 10.1.6](#).
- **Suspected transmission of an infectious agent via BRV**
- **Suspected adverse reaction associated with a suspected or confirmed falsified medicinal product or quality defect (combined complaint) of BRV**
- **Unexpected therapeutic effect**

Note: Reports of off-label use, misuse, abuse, medication error, occupational exposure, lack of drug effect, overdose, transmission of infectious agent, falsified medication, or unexpected therapeutic effect should be reported as described in [Section 10.1.8](#) if considered medically important events by the treating physician.

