### **10.1.3 Reporting and description of AEs or other safety relevant information**

In order to ensure complete safety data collection, all AEs and other safety relevant information occurring during the study (ie, after signing the Patient Data Consent form), must be reported. This includes all AEs not present prior to the initial visit and all AEs that recurred or worsened after the initial visit (eg, underlying or previous concomitant disease).

Signs or symptoms of the condition/disease for which the prescribed treatment is being studied should be recorded as AEs only if their nature changes considerably or their frequency or intensity increases in a clinically significant manner as compared to the clinical profile known to the treating physician from the patient's history or the Baseline Period.

When recording an AE, the treating physician should use the overall diagnosis or syndrome using standard medical terminology, rather than recording individual symptoms, signs, or medical procedures. The Adverse Event Report form for NIS and source documents should be consistent.

Details for completion of the Adverse Event Report form for NIS are described in the AE reporting instructions.

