#### **10.1.6 Overdose of prescribed treatment**

Overdose of prescribed treatment refers to the administration of a quantity of a medicinal product given per administration or cumulatively which is above the maximum recommended dose according to the authorized product information.

Overdose should be reported on the Adverse Event Report form for NIS, independently of whether there is an AE associated with the excessive dosing or not.

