### **10.1.8 Procedures for reporting AEs or other safety relevant information**

The patient will be given the opportunity to report AEs spontaneously. A general prompt will also be given at each study visit to detect AEs, for example:

“Did you notice anything unusual about your health (since your last visit)?”

In addition, the treating physician should review any self-assessment procedures (eg, epilepsy/seizure diary, questionnaires) employed.

If an AE or other safety relevant information is reported, UCB must be informed within 1 working day of receipt of this information by the site (see contact information for AE reporting listed in the contact information for AE transmission of the NIS protocol). The treating physician must forward to UCB (or its representative) a duly completed Adverse Event Report form for NIS provided by UCB, even if the data are incomplete or if it is obvious that more data will be needed in order to draw any conclusions. Information recorded on this form will be entered into the global safety database.

If clarifications on the AE or other safety relevant information are necessary, UCB shall request additional information from the treating physician.

The Adverse Event Report form for NIS and other requested information must be provided in English.

Additional information (eg, autopsy or laboratory reports) received by the treating physician must be provided within 1 working day.

All documents in the local language must be accompanied by a translation in English, or the relevant information included in the same document must be summarized in the Adverse Event Report form for NIS.

The treating physician is specifically requested to collect and report to UCB (or its representative) any AEs or other safety relevant information, and to also inform participating patients of the need to inform the treating physician of any AE or other safety relevant information during the study.

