### **3.5 Analysis sets**

The All Subjects Documented set is defined as all patients included in the study with valid data consent and for whom at least Visit 1 (Baseline) is documented. The All Subjects Documented set will be used for patient disposition and patient data listings only.

The Safety Set (SS) is defined as all patients included in the All Subjects Documented set for whom it cannot be excluded that they received treatment with BRV at least once in the study. Evidence of BRV dosing will be determined based on patients meeting 1 or more of the following criteria:

- At least 1 entry with a total daily dose >0 recorded in the BRV Medication (NIS) CRF page
- A present date of first BRV administration during observational study, recorded in the First Administration of BRV CRF page
- A present date of last BRV administration while in the study, recorded in the Study Termination (Dropout) or Study Termination (Completed Subject) CRF pages

The SS will be used for the summary of the safety data, Baseline characteristics of the patients, and important protocol deviations.

The Full Analysis Set (FAS) is defined as all patients in the SS who did not receive BRV before entering this NIS. Any patients with a documented protocol violation of Selection Criterion #1 will be considered to have been treated with BRV prior to inclusion in this NIS and will be excluded from the FAS. The FAS will be used for the analysis of BRV retention (ie, the primary variable), the secondary variables, and other variables.

The modified FAS is defined as all patients in the FAS who are treated according to the approved SmPC during their Observation Period, representing the on-label use of BRV. Compliance with the approved SmPC is defined as follows:

- Patient has POS with or without secondary generalization at Baseline (ie, patient does not have a protocol violation of Selection Criterion #5)
- All documented BRV doses were less than or equal to the maximum approved dose of 200mg/day
- BRV doses were greater than or equal to the minimum approved dose of 50mg/day (with the exception of down-titrating). Per the SmPC, a down-titration of BRV is allowed to 20mg/day, hence any patients receiving BRV doses lower than 50mg/day from day 2 onwards will be reviewed during the DEM to determine whether they are taking BRV per SmPC.

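### The Note in protocol 10.1.2 makes reporting of other safety relevant items depend on medical importance, against 10.1.3 and 10.1.8, so these reports may be incomplete and uneven across sites

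*Protocol*

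**What the plan says.** Five places in the current protocol govern the reporting of OSR information.

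- **10.1.2, Note.** The items covered begin "Reports of off-label use, misuse, abuse, medication error, occupational exposure, lack of drug effect, overdose, transmission of infectious agent" and go on to falsified medication and unexpected therapeutic effect. They should be reported as in 10.1.8 "if considered medically important events by the treating physician".
- **10.1.3.** To make safety data collection complete, "all AEs and other safety relevant information occurring during the study (ie, after signing the Patient Data Consent form), must be reported".
- **10.1.8.** The treating physician is asked to "collect and report to UCB (or its representative) any AEs or other safety relevant information".
- **10.1.6.** Overdose should go on the Adverse Event Report form for NIS "independently of whether there is an AE associated with the excessive dosing or not".
- **8.2.** "When the primary reason for withdrawal is lack of effectiveness or an AE, both must be reported as described in" Section 10.1.8.

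SAP 10.2 takes AEs and OSR information from the sponsor's pharmacovigilance database. It uses OSR information in one category of the overview table, a glossary and by-patient listings. Protocol 10.1.7 provides for periodic review of reported AEs together with other safety information.

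**The concern.** Two thresholds are in force for the same items. Under the Note, the physician's view of medical importance decides whether anything is sent. Under 10.1.3 and 10.1.8, everything is sent. Protocol section 5 plans for "approximately 100 sites in approximately 10 European countries", and section 13.1 limits on-site monitoring to for-cause visits, so differing readings could persist unnoticed.

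At stake is whether OSR counts mean the same thing at every site. A low count could reflect few events or a stricter reading of the Note, and the report could not tell these apart. The counts could also disagree with the study's own eCRF tables of doses and discontinuation reasons, with no explanation available.

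**Working it through.** The plan gives no figure to reproduce here. The check is a comparison of text, followed by an illustration of size.

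**Step 1: same items.** The Note names overdose and lack of drug effect along with the rest of the 10.1.2 list. These are the items that 10.1.3 and 10.1.8 call other safety relevant information.

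**Step 2: same route.** The Note and 8.2 both point to 10.1.8, which requires the Adverse Event Report form for NIS and sets a limit of 1 working day. Section 10.1.6 names the same form. The Note therefore cannot be read as governing a separate, faster channel.

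**Step 3: the Note against each section.**

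- *10.1.3 and 10.1.8:* a contradiction for every listed item. They cover all such information; the Note covers only what the physician considers medically important.
- *10.1.6:* a mismatch for overdose. The section expressly waives only the need for an accompanying AE. It is silent on importance, so it has no filter where the Note has one.
- *8.2:* a mismatch in one situation only, where lack of effectiveness is the primary reason for withdrawal. For lack of effect in a patient who stays on treatment, the conflict is with 10.1.3 and 10.1.8.

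**Step 4: precedence.** No section says which rule prevails. For a medication error without harm, one site could send a form and another send nothing, and each could cite the protocol.

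**Step 5: would the analysis reveal it?** SAP 10.2 plans a listing of records that could not be reconciled, but defines these as safety records whose patient number is absent from the clinical database. It would not find the reverse case: an eCRF dose above the maximum, or a dropout for lack of efficacy, with no safety record.

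**Step 6: size, under assumptions only.** Let *s* be the share of OSR events arising at sites that apply the Note, and *f* the fraction of those events judged medically important. Assume that all other sites report everything. Then

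captured / true = (1 − *s*) + *s* × *f* = 1 − *s*(1 − *f*).

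Neither input is in the documents. Over an assumed range:

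- *s* = 0.25, *f* = 0.8: 1 − 0.25 × 0.2 = 0.95
- *s* = 0.50, *f* = 0.5: 1 − 0.50 × 0.5 = 0.75
- *s* = 0.75, *f* = 0.2: 1 − 0.75 × 0.8 = 0.40

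If no site applies the Note (*s* = 0), the ratio is 1. Applying the Note can only remove reports, but the documents do not show how often this happens, if at all.

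**The case against.** The case on the other side has real substance.

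- **Overdose.** The overdose bullet in 10.1.2 itself refers the reader to 10.1.6. A site that follows the cross-reference reaches a rule with no importance test. It would be wrong to say that a site reading 10.1.2 sends nothing, or that 10.1.6 states the literal opposite of the Note. This stands. The Note still names overdose, so 10.1.2 gives two signals.
- **Withdrawal for lack of effectiveness.** A site can obey both texts by reporting every such withdrawal under 8.2 and using judgement otherwise. This stands for 8.2, but does not help with 10.1.3 and 10.1.8.
- **Site practice.** Section 10.1.3 mentions separate AE reporting instructions that are not among the documents. They may give sites a single rule. This is a reason for caution about consequences; the protocol text still conflicts.
- **Limited reach.** OSR information is not among the safety variables in protocol 4.4. Discontinuation reasons are tabulated under SAP 5.1 and doses above 200mg under SAP 10.1, so part of the information survives elsewhere. This stands, and it is also what makes a cross-check possible.
- **Timing.** SAP 4.3 records all three snapshots as done, the last with a cut-off of 28 Nov 2019. New instructions to sites may come late. The data check would still help.

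A reader might also go further and infer a number of lost reports. With 530 patients and 50% retention, 530 × 0.50 = 265 are not retained. If 20% to 50% of these left for lack of effectiveness, that is 53 to 133 patients, set against as few as 0 reports under the Note. The documents do not support this. The 50% is the proportion used for the confidence interval width in protocol 12.4, the 20% to 50% share is an assumption, and zero reports requires a site to disregard 8.2. The figures count withdrawals, not missing forms.

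**Conclusion.** The inconsistency is real and stands in current text. The Note contradicts 10.1.3 and 10.1.8 for every listed item and does not match 10.1.6 or 8.2. OSR reports may therefore be incomplete and uneven between sites.

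The size is unknown. The range of 0.95 down to 0.40 captured rests wholly on assumed inputs and is no estimate of loss. A reader might conclude that these events will be under-reported, or that the counts are biased downward and uninterpretable. That goes too far, because no document shows that any site applies the filter.

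The consequences reach the OSR category of the overview table, the OSR listing and glossary, and signal review. Retention, the seizure outcomes and the tables of treatment-emergent AEs and ADRs do not depend on it. The point merits correction because the remedy is cheap and improves the completeness of safety data.

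**What to change.** 1. **Reconcile the text.** Bring the 10.1.2 Note into line with 10.1.3, 10.1.6, 10.1.8 and 8.2, so that one stated reporting threshold applies to every listed OSR item. Changing the Note only for overdose and for withdrawal due to lack of effect would leave off-label use, misuse, abuse, medication error and the rest still in conflict with 10.1.3 and 10.1.8. Tell sites by clarification or memo. The sponsor should decide whether this counts as a significant change needing an amendment under protocol 14.4.

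2. **Cross-check existing data before database lock.** List patients with any eCRF daily dose above the ceiling in SAP 3.5 ("All documented BRV doses were less than or equal to the maximum approved dose of 200mg/day") and patients whose dropout reason is lack of efficacy. Compare both lists with the pharmacovigilance OSR records and query each patient found in one source only. Since SAP 10.2 imports only reportable events, make the comparison before that filter, or note it as an explanation. Describe any remaining mismatch in the study report.

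The check covers only what the eCRF captures. It will not find an overdose or medication error that was never entered, so the text still needs correcting.

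The cost is a short clarification, one program run on data already collected, and some additional forms and queries for sites.

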### **10.1.3 Reporting and description of AEs or other safety relevant information**

In order to ensure complete safety data collection, all AEs and other safety relevant information occurring during the study (ie, after signing the Patient Data Consent form), must be reported. This includes all AEs not present prior to the initial visit and all AEs that recurred or worsened after the initial visit (eg, underlying or previous concomitant disease).

Signs or symptoms of the condition/disease for which the prescribed treatment is being studied should be recorded as AEs only if their nature changes considerably or their frequency or intensity increases in a clinically significant manner as compared to the clinical profile known to the treating physician from the patient's history or the Baseline Period.

When recording an AE, the treating physician should use the overall diagnosis or syndrome using standard medical terminology, rather than recording individual symptoms, signs, or medical procedures. The Adverse Event Report form for NIS and source documents should be consistent.

Details for completion of the Adverse Event Report form for NIS are described in the AE reporting instructions.

